Skeletal Physiology Dysregulation in Obesity: The Role of Growth Hormone

NCT# 01724489

Version Date: November 7th, 2019

PARTNERS HUMAN RESEARCH COMMITTEE PROTOCOL SUMMARY

Answer all questions accurately and completely in order to provide the PHRC with the relevant information to assess the risk-benefit ratio for the study. Do not leave sections blank.

PRINCIPAL/OVERALL INVESTIGATOR [name]

PROTOCOL TITLE

Skeletal Physiology Dysregulation in Obesity: The Role of Growth Hormone

FUNDING

VERSION DATE 10.16.19

SPECIFIC AIMS

Concisely state the objectives of the study and the hypothesis being tested.

Specific Aim 1: Low-dose GH administration for 18 months to osteopenic obese men and women will increase bone mass, improve bone microarchitecture and increase bone strength.

We will investigate in osteopenic men and women with obesity and relative IGF-1 deficiency, whether GH administration for 18 months to increase IGF-1 levels within the normal range results in:

- A. Increased BMD
- B. Improved bone microarchitecture, including trabecular and cortical thickness.
 - The increase in trabecular thickness will be mediated primarily by GH and the effect on cortical thickness by IGF-1
- C. An increase in bone strength, as determined by finite element analysis

Specific Aim 2: We will investigate mechanisms responsible for the increase in bone strength due to GH administration. We hypothesize that the increase in strength will be mediated by:

- **A.** A reduction in bone marrow fat mediated by a decrease in Pref-1 associated with an increase in osteoblast activity, assessed by markers of bone formation, including P1NP
- B. Increased insulin, in associations with an increase in undercarboxylated osteocalcin
- **C.** Improved body composition, including a decrease in abdominal adiposity and lipid deposits in muscle and liver, and an increase in muscle mass
- D. A reduction in inflammatory cytokines and improvement in the serum lipoprotein apoB
- E. An increase in circulating vitamin D.

BACKGROUND AND SIGNIFICANCE

Provide a brief paragraph summarizing prior experience important for understanding the proposed study and procedures.

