- Blood drawn to determine levels of hormones and other chemicals (3 week, 9 week, 4 month, 6 month, 9 month 12 month, 15 month, 18 month and 24 month visits).
- OGTT (6 month, 12 month, and 18 month and 24 month visits)
- Paffenbarger Physical Activity Questionnaire and Calcium & Vitamin D Frequency Questionnaire (6-month, 12-month, 18-month, 24-month visits)
- Functional Strength Test (6-month, 12-month, 18-month and 24-month visits)
- Food diary log (18-month visit)

	-	0	
-			
•			
-			

*discontinued performing starting in August 2017

Study endpoints

Aim 1:

Primary Endpoint: Change in BMD over 18 months in the GH vs placebo group.

Secondary Endpoints:

- 1. Bone microarchitectural parameters
- 2. Bone strength by FEA

Aim 2:

Primary Endpoint: Change in bone marrow fat in the GH vs placebo group. **Secondary Endpoints:**

- 1. Pref-1.
- 1. Bone formation markers P1NP, ucOC.
- 2. Fasting and 2-hour OGTT insulin.
- 3. Inflammatory markers hsCRP, TNF1 receptor, and IL-6.
- 4. Serum lipoproteins.
- 5. 25-OH vitamin D.

Dual-energy X-ray-absorptiometry (DXA): DXA will be used to measure BMD of the AP and lateral spine (L1-L4), distal radius, total hip, femoral neck and total body. Total fat and fat-free mass measurements will also be obtained.

Quantitative computed tomography (QCT): As DXA may overestimate BMD in obesity,¹⁰⁷ we will perform volumetric QCT of L1 and L2 and of the proximal femur (GE LightSpeed Pro CT scanner, GEHealthcare, Waukesha, WI or Somatom Definition, Siemens Healthcare, Forchheim Germany) and low-dose single slice CT of the abdomen and thigh for body composition.

High-resolution CT: High resolution peripheral QCT will be used to measure volumetric density, morphology and microarchitecture at the distal radius and distal tibia (XtremeCT, Scanco Medical AG[®], Bassersdorf, Switzerland). The outcome variables computed by automated analysis will include volumetric BMD (g hydroxyapatite/cm³) for total, trabecular, and cortical regions; cortical thickness (µm) and porosity measures and trabecular number (mm-1), thickness (mm), and separation (mm). HR-pQCT measurements will be performed at the non-dominant wrist and leg in the absence of a history of fracture.

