Subjects will have DXAs of the total body, PA and lateral spine, hip and radius at up to 5 visits. Also, QCT scans of L1 and L2 and of the proximal femur at 2 visits. Subjects will also have an XtremeCT of the ultradistal radius and distal tibia at 4 visits. They will also undergo low dose CTs of the thigh and abdomen at three visits. Some subjects may undergo a wrist X-ray at the screening visit and a head X-ray prior to the baseline MRI. The combined radiation from all these aforementioned procedures for the entire study is approximately 4.757 mSv – this amount of radiation is equal to approximately 19 months of natural background radiation. Blood drawing may result in bruising or infection at the venipuncture site.

MRS and MRI will be performed using FDA approved devices and pulse sequences. There are no known foreseeable risks associated with exposure to MRI, provided there are no metallic implants (i.e., vascular clamps or pacemakers). All potential subjects will be screened for the presence of such prior to the exam. Some subjects do report some claustrophobia during the scan. If a patient expresses any discomfort during the scan, the procedure will be aborted and not repeated without his/her full consent. Subjects will be required to lie in a magnet for about 1 hr. The 3.0T MR device is FDA-approved for clinical use. No serious or lasting side effects associated with the use of MRI have been reported. Rarely, subjects report sensations such as vertigo and a metallic taste when exposed to magnetic fields. Minor theoretical hazards arise from rapid gradient switching and RF transmission. All parameters used for conventional and spectroscopic imaging fall within FDA limits for specific absorption rates (SAR) of RF transmission and rapid gradient switching (dB/dt). Experiments properly conducted in compliance with FDA, OSHA and standard safety practices of the MGH-NMR Center pose no significant risk to research subjects. MR examinations will be performed by a Radiological Technologist certified by the Commonwealth of Massachusetts. Any adverse events will be reported immediately to the MGH Human Research Committee.

Partners Human Subjects Research Application Form Version Date: June 1, 2005 Filename: Protocol Summary 9

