
**Data analysis plan:** We will pool data from men and women using a random slopes model; we will consider a model where each patient has a random slope and intercept. The mean intercept and slope may be different for men and women and in each treatment group. The primary analysis is a pooled analysis of treatment effect across gender with weights equaling the frequency of men and women in the sample. A secondary analysis will test for the significance of the treatment-gender interaction on the rate of change of BMD and all other endpoints. For all analyses, an intent-to-treat analysis will be performed. We plan to apply the guidelines developed by the National Research Council regarding missing data. Our primary analysis, the random slopes model, assumes that data is missing at random. We also will conduct two sensitivity analyses. The first assumes that the missing data is a function of the unobserved random effect and the second tests the assumptions in this model under other missingness mechanisms. We will also determine which of the secondary endpoints appears to mediate the treatment effect on an endpoint, such as BMD, microarchitectural parameters, and bone marrow fat by examining the effect of treatment on the potential mediator and of the potential mediator on the endpoint; examples of this will include whether Pref-1 mediates the effects of GH on bone marrow fat or strength, and whether bone marrow fat, body composition variables, inflammatory markers, lipids or vitamin D mediate the effects of GH on bone strength. The effect on one endpoint by a potential mediator is the product of the two effects. The Sobel test will test whether this effect is zero. As there are no known moderators of GH treatment in this population and the population has been purposely selected for osteopenia, we will not control for covariates other than gender in our primary analysis. We will perform exploratory analyses to answer the following: 1. Among an osteopenic population are there covariates

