(such as family history, smoking, alcohol, exercise, free testosterone or estradiol) that predict problems such as anomalies in bone microarchitecture and predicted strength? 2. Are these factors moderators of the treatment effect of GH? Both of these analyses will use stepwise variable selection using a random effects model as above. 3. Is the effect of GH on BMD mediated by IGF1? We will perform a mediation analysis using a random effects model with final GH dose and a final GH dose time interaction in the treated group.

**Timeline:** Screening, enrollment, and study visits will occur from year 1 through year 5. Data management will occur in years 1-5, and analyses and manuscript preparation will be performed in years 4-5.

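### No season term is planned for 25-OH vitamin D: the GH-placebo contrast stays unbiased, but if the analyte is seasonal some precision is lost and the vitamin D mediation path is attenuated

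*SAP*

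**What the plan says.** Protocol, Specific Aim 2, item E, hypothesises "An increase in circulating vitamin D", and the Study endpoints section lists "25-OH vitamin D" among the Aim 2 secondary endpoints. The Aim 2 primary endpoint is framed against a concurrent comparator: "Change in bone marrow fat in the GH vs placebo group".

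The blood-draw item under Follow-up visits gives the post-baseline times as "3 week, 9 week, 4 month, 6 month, 9 month 12 month, 15 month, 18 month and 24 month visits". Vitamin D appears in the endocrine testing list without a visit schedule of its own.

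SAP, Data analysis plan: "we will consider a model where each patient has a random slope and intercept". Means may differ by sex and arm, and the rate of change is the quantity of interest for BMD and the other endpoints. The primary analysis adjusts for gender only. The exploratory covariates (family history, smoking, alcohol, exercise, sex hormones) do not include season or draw date. The mediation analyses ask "whether bone marrow fat, body composition variables, inflammatory markers, lipids or vitamin D mediate the effects of GH on bone strength", using a Sobel test.

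SAP, Timeline: "Screening, enrollment, and study visits will occur from year 1 through year 5". The Protocol's risk section places the MR examinations with staff "certified by the Commonwealth of Massachusetts", which suggests one northern location. Neither document mentions seasonality.

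**The concern.** If 25-OH vitamin D rises and falls over the year, a patient's fitted slope depends partly on the month of entry. Months 6 and 18 are half a year out of phase with baseline; months 12 and 24 are in phase. Over an 18-month window, a patient who enters near the seasonal peak tends to show a fall and one who enters near the trough tends to show a rise, whatever GH does. With entry dates spread over several years, this becomes extra between-patient variation in slope.

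Two results are exposed. The Aim 2E comparison loses power. In the mediation analysis, seasonal variation acts as error in the mediator and flattens the estimated relation between vitamin D and strength. A null vitamin D mediation result would then be hard to interpret.

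**Working it through.** **The plan's own figures.** With 50 completers (25 per arm, 1:1 assumed), 80% power and two-sided 0.05, the t-based detectable difference is 0.809 SD, which agrees with the SAP's 0.81 SD for bone marrow fat. The SAP's vitamin D figure, 0.025 ng/ml per year, cannot be reproduced because no SD is given. It would imply a slope SD of 0.025/0.81 = 0.031 ng/ml per year. The SAP gives the same number for hsCRP in mg/l, so value and unit need confirming. I do not use it as a noise input.

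**Assumptions (not in the documents).** Seasonal amplitude A = 2-6 ng/ml around the yearly mean, central 4; non-seasonal within-patient SD 5-7 ng/ml; true between-patient slope SD 0-4 ng/ml per year; entry dates uniform over the year; one seasonal curve common to all patients.

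**Seasonal part of a patient's slope.** Take visits at 0, 0.5, 1 and 1.5 years. The mean is 0.75 and Sxx = 1.25, so the least-squares weights are -0.6, -0.2, 0.2, 0.6. A cosine that peaks at baseline takes values A, -A, A, -A, giving a false slope of (-0.6 + 0.2 + 0.2 - 0.6)A = -0.80A per year. Over uniform entry dates its variance is (0.80A)²/2 = 0.32A², which is 5.12 at A = 4.

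**Share and power.** Residual slope variance is SD²/Sxx: 25/1.25 = 20.0, or 49/1.25 = 39.2. Share = seasonal variance / (seasonal + residual + true slope variance). Power = Φ(2.80·√(1 - share) - 1.96). For SD 5 and slope SD 0, share = 5.12/25.12 = 20.4% and power = Φ(2.80 × 0.892 - 1.96) = 70.5%.

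The Protocol gives two sets of early visit times (3 week/9 week/4 month, and 6 week/3 month/4.5 month), so both were run. Results at A = 4, as share / power:

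| Draws used | Residual SD | Slope SD 0 | Slope SD 4 |
|---|---|---|---|
| 0, 6, 12, 18 months | 5 | 20.4% / 70.5% | 12.5% / 74.6% |
| | 7 | 11.6% / 75.0% | 8.5% / 76.4% |
| 3 wk, 9 wk, 4 mo list, to 18 months | 5 | 26.6% / 67.0% | 12.7% / 74.5% |
| | 7 | 15.6% / 73.0% | 9.5% / 76.0% |
| 6 wk, 3 mo, 4.5 mo list, to 18 months | 5 | 19.3% / 71.1% | 9.1% / 76.2% |
| | 7 | 10.9% / 75.3% | 6.7% / 77.2% |
| 3 wk, 9 wk, 4 mo list, plus month 24 | 5 | 4.7% / 78.1% | 1.3% / 79.5% |
| | 7 | 2.4% / 79.0% | 1.1% / 79.6% |

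On 0/6/12/18/24 months the seasonal slope is exactly zero. For visits to 18 months, power runs from about 77% to 79% at A = 2 and from about 55% to 74% at A = 6.

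**Bias and error rate.** In 20,000 simulated trials per setting (25 per arm, slope SD 2, residual SD 3, A from 0 to 8), bias in the GH-placebo slope difference was at most 0.015 ng/ml per year and type I error was 0.048-0.052. This held when entry clustered in one season: both arms shift equally. On 0/6/12/18 months the standard error of the arm difference rose from 0.95 at A = 0 to 1.24 at A = 5.

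**Mediation.** With an assumed true mediator, a GH effect of 5 ng/ml per year and a non-seasonal bone endpoint, taking A from 0 to 5 on 0/6/12/18 months lowered the mediator-outcome coefficient from 0.107 to 0.062 and Sobel power from 0.54 to 0.26. Using all listed draws to 18 months, Sobel power fell from 0.73 to 0.42. With no true mediation, rejection stayed at about 4% or below.

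**The case against.** The best case against is that this is an optional refinement for one secondary endpoint and one of several candidate mediators. Gender-only adjustment is a reasoned choice, stated for the primary analysis. The amplitude is an outside assumption, and year-round entry at one location is inferred. True between-patient slope variance, which the SAP's model expects, dilutes the seasonal share. If month 24 enters the slope, almost nothing is lost. All of that stands and keeps the severity low. Against it, the SAP treats months 18-24 as a withdrawal period, so an on-treatment slope would naturally stop at 18 months, and the remedy costs almost nothing.

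A reader might also infer more than the documents support:

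- *That vitamin D is tested only at 6 and 18 months, in the opposite season.* The Protocol lists hormone and chemistry draws at nine post-baseline visits, including months 12 and 24.
- *That season is mistaken for a GH effect.* It distorts a single patient's slope or a single-arm change, but the contrast with concurrent placebo is unbiased if entry season is balanced between arms in expectation.
- *That season creates a false mediator signal.* The main effect is attenuation. In the simulations, a spurious signal (7-31% rejection) appeared only when GH truly raised vitamin D and the bone endpoint was also assumed seasonal.
- *That a vitamin D withdrawal comparison is affected.* The SAP describes the 24-month comparison for BMD only.
- *That the loss should be judged on baseline-to-18-month change.* That contrast would suffer more, but the SAP plans slopes, not change scores.

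**Conclusion.** The point holds as a matter of precision. The SAP has no season or draw-date term for 25-OH vitamin D. If the analyte is seasonal with amplitude near 4 ng/ml, a slope comparison that would have 80% power without seasonal noise keeps about 67-77% with visits to 18 months and about 78-80% with month 24 included. The vitamin D-to-strength mediation path is attenuated, so a negative mediation finding would carry less weight.

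These sizes rest on assumed amplitude, residual SD and slope SD, uniform entry and a common seasonal curve; with a small amplitude the loss is negligible. Absence of bias rests on entry season being balanced between arms in expectation. Neither the primary BMD result nor the validity of the GH-placebo test for vitamin D is in question. Severity is low.

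**What to change.** Add one sentence to the Data analysis plan: in the model for 25-OH vitamin D, and in any mediation model that uses vitamin D, include the sine and cosine of the day of year of each blood draw as fixed terms common to both arms. State whether month 24 enters the vitamin D slope, since the size of the seasonal effect depends on it. As a supporting result, report the 12-month GH-placebo difference, in which baseline and follow-up fall in the same season to within the one-month visit window.

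The cost is two degrees of freedom and no new visits or assays. It needs the actual draw dates, which a study with scheduled visits should hold. Patient-specific seasonal amplitude would remain as noise. Fixing the terms before unblinding avoids a post hoc choice.

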Briefly describe study design and anticipated enrollment, i.e., number of subjects to be enrolled by researchers study-wide and by Partners researchers. Provide a brief summary of the eligibility criteria (for example, age range, gender, medical condition). Include any local site restrictions, for example, "Enrollment at Partners will be limited to adults although the sponsor's protocol is open to both children and adults."

Over the five years of this proposal, we expect to screen 300 patients in order to enroll 75 (38 healthy women and 37 healthy men) total men and women with obesity, osteopenia and relatively low IGF-1, adiposity for an evaluable 50 subjects. We will attempt to replace subjects who have dropped out of the study to ensure 50 completers at 18 months (for which the study is powered).

Eligibility:

Subjects will undergo a pre-study screening visit to determine eligibility for the study.

Inclusion criteria:

- Ages 18-65 and generally healthy
- $BMI \ge 25 \text{ kg/m}^2$

Partners Human Subjects Research Application Form Version Date: June 1, 2005

- BMD T or Z-score \leq -1.0 (as measured by DXA)
- IGF-I within or below the mean (plus 10% above the mean) for age and gender **Exclusion criteria**
- For women: amenorrhea for 3 months or more if premenopausal, pregnancy or breastfeeding, polycystic ovary syndrome
- Elevated creatinine or TSH levels; alanine amino transferase levels greater than 2 times the upper limit of normal
- History of diabetes mellitus, cancer or other serious chronic disease
- Use of osteoporosis medications
- Medication that could affect bone metabolism within the past three months, such as chronic oral glucocorticoids, gonadal steroids, or anticonvulsants
- Hct > 5 units below the lower limit of normal
- Routine MRI exclusion criteria including the presence of pacemaker or cerebral aneurysm clips
- Osteoporosis, that, according to WHO classification (BMD T score less than or equal to 2.5 at the AP spine, total hip or femoral neck), would warrant treatment consideration.

Briefly describe study procedures. Include any local site restrictions, for example, "Subjects enrolled at Partners will not participate in the pharmacokinetic portion of the study." Describe study endpoints.

Screening Visit: (n=300: 150 healthy obese women and 150 healthy obese men)

- A complete medical history, physical examination, height, weight, waist and hip circumferences. Calculation of BMI, waist:hip ratio.

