## Statistical Power and Statistical Analysis

**Statistical power:** For Aim 1, primary endpoint, with an n=75 and 50 completers, we will have >80% chance of detecting a difference in the rate of BMD AP lumbar spine increase of 0.024g/cm^2/y at a 2-sided  $p=0.05$  level. This compares favorably with the rate of BMD AP spine increase of 0.036 g/cm^2/y in a study by Baum *et al.* administering GH for 18 months to hypopituitary subjects with GH deficiency. This was calculated with software developed by co-investigator [REDACTED] for sample size for random slopes models, available in Matlab [REDACTED]. The variance covariance matrix of the random effects,  $\Psi$ , and residual variance,  $\sigma^2$ , were estimated from longitudinal data from Baum *et al.* that had originally been analyzed by [REDACTED]. The variance of the intercept was 0.024, slope 0.000211, covariance 0.00199 and residual variance,  $\sigma^2$ , 0.00092 and an exponential drop-out rate of 0.36/yr, which is greater than we expect. The program uses the fact that the variance covariance matrix for the fixed effects of the model are:  $\mathbf{V(B)} = \{\mathbf{X}'[\sigma^2] + \mathbf{Z\Psi Z}'\}^{-1}\mathbf{X}$ . One incorporates drop outs by replacing  $\mathbf{X}'[\sigma^2] + \mathbf{Z\Psi Z}'\}^{-1}\mathbf{X}$  by a weighted sum for different follow-up times with weights equal to the follow-up probability -- a special case of the general model described in Pinheiro and Bates. For Aim 2, primary endpoint, with 50 completers we can detect 0.81 x SD of the difference in bone marrow fat content over a year; For secondary endpoints: for trabecular thickness (TbTh) and cortical thickness (CoTh), based on our preliminary data in obese men receiving placebo for 6 months in which the standard deviation (SD) of the change in TbTh was 0.0047mm and of CoTh was 0.0015mm, we will be able to detect an annual increase of 0.008mm and 0.012mm, respectively; for FEA we will have a power of 80% at a two-sided  $p=0.05$  significance level, if the true rate of difference in estimated failure load between the treatments is 316 units, based on an assumption that the SD is 570 units, as derived from Boutroy *et al.* With 50 completers, we will have an 80% power at a 2-sided  $p=0.05$  level to see a difference in PINP of 38.6 ng/ml, total abdominal fat of 50.8 cm^2, lean mass of 1.2 kg, vitamin D of 0.025 ng/ml, hsCRP of 0.025 mg/l, and apoB of 18.6 mg/dl per year. These were calculated from our preliminary data administering GH to obese subjects for 6 months. The power for the mediation analyses (see below) depends on the effect size of the treatment on BMD and on the correlation of the secondary endpoint on BMD. We derived a formula using the delta method. With at least 40 subjects we will have an 80% chance of achieving significance at a two-sided  $p=0.05$  level if the effect size is 2 units and the correlation is 0.5. For the 6-month withdrawal period, we will have adequate power to test whether the BMD remains significantly different from placebo at 24 months. We will have 80% power to detect a difference of 0.04 g/cm^2 assuming that there are at least 43 patients still in the study at 18 months (we expect 50).

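### If allocation was random, the primary random-slopes model gives up a little precision (0 to about 6% of variance in the cases run) by letting mean baseline BMD differ between arms

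*SAP*

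**What the plan says.** The SAP (Data analysis plan) fits a random intercept and slope for each patient and adds that "The mean intercept and slope may be different for men and women and in each treatment group". The treatment effect is then pooled across sex with "weights equaling the frequency of men and women in the sample". Gender is the only covariate in the primary analysis. Nothing in the supplied text sets the baseline mean equal across arms or adjusts for baseline BMD.

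The Protocol (Study endpoints, Aim 1) defines the primary endpoint as "Change in BMD over 18 months in the GH vs placebo group". The supplied text does not state random allocation or give a ratio. It is inferred from the GH-versus-placebo comparison and from the SAP's statement that "For all analyses, an intent-to-treat analysis will be performed".

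For power, the SAP gives these components: "The variance of the intercept was 0.024, slope 0.000211, covariance 0.00199 and residual variance" 0.00092. They come from a study "administering GH for 18 months to hypopituitary subjects with GH deficiency".

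**The concern.** Baseline BMD is measured before treatment. Under random allocation its expectation is the same in both arms within a sex, and any observed difference is chance. A model with a separate mean intercept for each arm treats that difference as an unknown to be estimated. A model with one intercept per sex uses the known equality. When the estimated intercept and slope are correlated, this sharpens the slope comparison.

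The stake is precision only. The SAP's power claim has almost no margin on its own components, so a couple of power points from scans already planned would be welcome. They would not change how the trial is judged.

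**Working it through.** **Inputs**
- SAP, Statistical power: intercept variance 0.024, slope variance 0.000211, covariance 0.00199, residual variance 0.00092; target difference 0.024 g/cm²/y; two-sided 0.05; n = 75 with 50 completers; drop-out 0.36/yr, described there as higher than expected.
- Protocol, Research Design and Methods and Follow-up visits: 38 women and 37 men; DXA at baseline, 12 and 18 months. The 24-month scan is left out because it follows withdrawal of treatment.
- Assumed: 1:1 allocation, and the same exponential loss in both arms. Having 50 of 75 left at 18 months implies a rate of −ln(50/75)/1.5 = 0.270/yr. At 0.36/yr, 75 × exp(−0.54) = 43.7 remain.

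**Formulas**

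Information per participant is M = Σ pₖ Z′(ZΨZ′ + σ²I)⁻¹Z, summed over the follow-up patterns {0}, {0, 1} and {0, 1, 1.5} years.

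Within a sex with arm sizes n₁ and n₂, the variance of the slope difference is:
- separate intercepts: (1/n₁ + 1/n₂) × M₁₁/(M₁₁M₂₂ − M₁₂²)
- one shared intercept: (1/n₁ + 1/n₂) / M₂₂

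The proportional cut is therefore M₁₂²/(M₁₁M₂₂), whatever the allocation ratio. At 1:1, pooling the sexes with weights 38/75 and 37/75 gives the multiplier (38/75)² × 4/38 + (37/75)² × 4/37 = 4/75 = 0.0533. Power = Φ(0.024/SE − 1.96).

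**Step 1: the SAP's own figure (50 of 75 completing)**

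The pattern weights are 0.237, 0.096 and 0.667, giving M₁₁ = 42.35, M₁₂ = −40.59 and M₂₂ = 766.4.
- Separate intercepts: 42.35/(42.35 × 766.4 − 40.59²) = 0.001374.
- Variance = 0.0533 × 0.001374 = 7.33 × 10⁻⁵, so SE = 0.00856.
- Power = Φ(2.803 − 1.96) = 80.0%, in line with the SAP's claim of just over 80%.

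**Step 2: one baseline mean per sex**
- 1/766.4 = 0.001305; variance = 6.96 × 10⁻⁵; SE = 0.00834.
- Power = Φ(2.877 − 1.96) = 82.0%.
- Cut = 40.59²/(42.35 × 766.4) = 5.1%, equivalent to about 0.051 × 75 = 3.8 participants.

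**Step 3: other loss rate and allocation ratio**

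| Loss | Allocation | Variance cut | Power, separate → shared |
|---|---|---|---|
| 50 of 75 completing | 1:1 | 5.1% | 80.0% → 82.0% |
| 0.36/yr | 1:1 | 4.5% | 75.7% → 77.6% |
| 50 of 75 completing | 2:1 | 5.1% | 75.3% → 77.4% |
| 0.36/yr | 2:1 | 4.5% | 70.8% → 72.7% |

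At 0.36/yr and 1:1, the SE goes from 0.00903 to 0.00882.

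**Step 4: a narrower baseline distribution**

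The Protocol bounds entry BMD on both sides. Inclusion requires a "BMD T or Z-score" of −1.0 or below, and the exclusion list removes "Osteoporosis, that, according to WHO classification". Suppose this shrinks the intercept variance to a fraction f. The documents do not give f, so a range is shown. The covariance is then multiplied by f, and the slope variance becomes 0.000211 − (0.00199/0.024)² × 0.024 × (1 − f).

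| f | Cut, 50 of 75 | Cut, 0.36/yr | Power, 50 of 75, 1:1 |
|---|---|---|---|
| 1 | 5.1% | 4.5% | 80.0% → 82.0% |
| 0.75 | 2.7% | 2.4% | 81.3% → 82.3% |
| 0.5 | 0.6% | 0.5% | 82.6% → 82.8% |
| 0.4 | 0.1% | 0.1% | 83.2% → 83.2% |
| 0.34 | 0 | about 0 | 83.6% → 83.6% |
| 0.2 | 1.1% | 1.0% | 84.6% → 85.0% |
| 0.1 | 5.9% | 5.4% | 85.8% → 87.7% |

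The gain vanishes where M₁₂ passes through zero, at f = 0.338 with 50 of 75 completing.

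**Step 5: a weaker intercept–slope covariance**

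The SAP's components imply a correlation of 0.00199/√(0.024 × 0.000211) = 0.88. Lowering only the covariance to 0.0015, 0.001, 0.0005 or 0 gives cuts of 2.0%, 0.3%, 0.1% or 1.3% (50 of 75 completing).

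**The case against.** The best case for leaving the plan alone has four parts.

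- **Materiality.** Arm-specific intercepts are a standard, valid choice that suits an endpoint defined as change, and the planned model already reaches the power the SAP claims. For f between 0.2 and 0.5, a range the entry criteria make plausible, the gain is at most 0.4 power points. This stands. It is why the point ranks as optional and why 5.1% should not be read as the expected gain.
- **Unverified premise.** Random allocation is inferred, not stated, in the text supplied, part of which was removed before review. Without it, the constraint could bias the slope difference, whereas the planned model is protected. This stands as a condition on the advice.
- **Timing.** The Protocol's schedule footnote shows procedures being dropped from August 2017, and the documents do not give the blinding status. Changing a primary model after data have been seen would cost more credibility than two power points are worth. This too stands as a condition.
- **Linearity.** If BMD change is not linear, the fitted intercept is not exactly the baseline mean. In late-onset and plateau scenarios on the SAP's components, the two models targeted slopes within about 1% of each other, so this carries little weight while the 24-month scan stays out of the slope.

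Also, 0 to 6% is the span of the cases shown and not a bound: with no drop-out the cut is about 7%. That no case lost precision is expected, because a correct constraint cannot lose precision when the variance components are known.

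**Conclusion.** The point holds as a minor, optional improvement. The primary model leaves a known equality unused, at a cost in precision and not in bias. If the SAP's components apply unchanged, the loss is 5.1% of the slope-difference variance with 50 of 75 completing, or 4.5% at 0.36/yr, which is about two power points in each case. If selection on BMD narrows the baseline spread, or the intercept–slope covariance is weaker than in the hypopituitary data, the loss may be negligible.

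The conclusion rests on random allocation, a linear trend over the 18 treatment months, equal loss in both arms, and exclusion of the 24-month scan from the slope. The percentage cut does not depend on the allocation ratio; the power figures do.

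**What to change.** First confirm that allocation was random and that no treatment-group data have been seen. If both hold, add a dated sentence to the SAP before unblinding: *mean baseline BMD may differ by sex but is constrained equal across treatment groups within sex; mean slopes may differ by sex and by treatment group.* Keep the separate-intercept model as a sensitivity analysis.

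If allocation was random but treatment-group data have been seen, keep the planned model as primary and report the constrained fit as the sensitivity analysis. If allocation was not random, leave the model as it is.

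The cost is one sentence and one extra model fit. No new data or visits are needed, and no covariate is added, so the plan to adjust only for gender is unaffected.
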